## **12. SAFETY REPORTING OF ADVERSE EVENTS**

### **12.1. General**

Safety assessments will consist of monitoring and appropriate reporting AEs and SAEs that are considered possibly, probably or definitely related to the **investigational treatment (i.e. to CB-839, or to the combination of CB-839 + panitumumab/irinotecan) and research F-FSPG PET/CT scans**, all events of death, and any study-specific issue of concern.

Adverse event collection and reporting is a routine part of every clinical trial. Each adverse event will be graded according to the NCI's Common Terminology Criteria for Adverse Events (NCI CTCAE), Version 4.03, dated June 14, 2010, currently locatable via the following URL:

[http://evs.nci.nih.gov/ftp1/CTCAE/CTCAE\\_4.03\\_2010-06-14\\_QuickReference\\_8.5x11.pdf](http://evs.nci.nih.gov/ftp1/CTCAE/CTCAE_4.03_2010-06-14_QuickReference_8.5x11.pdf)

For events not listed in the CTCAE, severity will be designated as mild, moderate, severe or life threatening, or fatal which respectively correspond to Grades 1, 2, 3, 4, and 5 on the NCI CTCAE, with the following definitions:

- **Mild:** An event not resulting in disability or incapacity and which resolves without intervention;
- **Moderate:** An event not resulting in disability or incapacity but which requires intervention;
- **Severe:** An event resulting in temporary disability or incapacity and which requires intervention;
- **Life-threatening:** An event in which the patient was at risk of death at the time of the event;
- **Fatal:** An event that results in the death of the patient.

Information on all adverse events, whether serious or not, whether reported by the participant, directly observed, or detected by physical examination, laboratory test or other means, will be collected, recorded, followed and reported as described in the following sections.

### **Reporting period**

Adverse events experienced by participants will be collected and reported from initiation of protocol-indicated treatment for Phase I patients. For Phase II patients, AEs will be collected and reported from the time of the first research scan. AEs will be tracked for all patients in both phases throughout the study through 28 days after the last dose of protocol-indicated treatment. Participants who experience an adverse event related to a study procedure and/or protocol-indicated treatment beyond 28 days will continue to be contacted by a member of the study team until the event is resolved, stabilized, or determined to be irreversible by the participating investigator.

Laboratory and vital sign abnormalities are to be recorded as Adverse Events only if they are medically relevant as judged by the investigator (e.g. symptomatic, requiring corrective treatment, leading to discontinuation and/or fulfilling a seriousness criterion). Unless otherwise specified by protocol or a patient's study physician, abnormal laboratory values of Grade 1 and Grade 2 will be deemed Not Clinically Significant (NCS) and are not required to be individually noted or recorded within the study data.

Baseline disease-related signs and symptoms which are initially recorded as medical history, will subsequently be recorded as adverse events during the trial if they worsen in severity or increase in frequency.

Participants should be instructed to report any serious post-study event(s) that might reasonably be related to participation in this study. The investigator should notify the IRB and any other applicable regulatory agency of any unanticipated death or adverse event occurring after a participant has discontinued or terminated study participation that may reasonably be related to the study.

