## 2.6.2 Rationale for $^{11}\text{C}$ -Glutamine PET/CT

Another leading PET tracer that provides a surrogate measurement of glutamine metabolism under active investigation at the Vanderbilt Center for Molecular Probes (CMP) is carbon-11-labeled glutamine ( $^{11}\text{C}$ -Glutamine; Figure 2). To reflect the uptake of glutamine in tumors, we will utilize  $^{11}\text{C}$ -Glutamine. This tracer is chemically and biologically identical to naturally occurring glutamine; via PET imaging,  $^{11}\text{C}$ -Glutamine will enable quantitative assessment of glutamine flux in tumors. Imaging with  $^{11}\text{C}$ -Glutamine will represent the first-in-human study of this tracer.

Patients that consent to  $^{11}\text{C}$ -Glutamine will be continuously monitored for the safety,

biodistribution and metabolism characteristics of C-Glutamine through the course of the study and it is anticipated that, after approximately 15 patients have received C-Glutamine, we will have collected sufficient data to pursue an IND submission.

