## 6. SCHEDULE OF ASSESSMENTS

### 6.1. Study Calendar

Protocol Activities 1 Cycle = 4 weeks (28 days)	Screening (Day -14 to Day -1)	CYCLE 1			CYCLES ≥ 2		Post-Treatment	
		Day 1	Day 15	Day 28 	Day 1 (± 1 day) 	Day 15 (± 1 day) 	EOT (≤ 14d after last treatment) 	Follow-Up (28d + 7d after last study dose) 
Assessments & Observations								
Consent, Baseline Characteristics & Eligibility 	X							
Physical and Skin Examination 	X	X 	X		X	X	X	X
ECOG Performance Status	X	X	X		X	X	X	X
Vital Signs	X	X	X		X	X	X	X
Height	X							
Weight 	X	X 	X		X	X	X	X
Review of Con Meds and Adverse Events 	X	X	X		X	X	X	X
Study Drug Compliance (Dosing Diary)			X	X	X		X	
DLT Evaluation (dose-escalation only) 		X	X	X	X			
Laboratory Assessments								
Hematology and Blood Chemistry 	X	X 	X		X	X	X	X
Urinalysis	X							
Pregnancy Test 	X	X		X			X	
Disease Assessments								
CT or MRI Scan 	X				X		X 	X 
 C-Glutamine PET/CT (Optional in Phase I only, not performed in Phase II) 	X 			X 				
 F-FSPG PET/CT (Optional in Phase I) 	X 			X 				
Survival Follow-Up								X 
Biospecimen Collections								
Research Tumor Biopsy (Phase II Only)	X							
Pharmacokinetic (PK) Blood (Optional in Phase I) 	X			X				
Pharmacodynamic (PD) Blood (Phase II Only) 		X		X			X	
Treatment								
CB-839 oral administration 		Continuous oral twice daily dosing 						
Panitumumab infusion 		X	X		X	X		
Irinotecan infusion (Phase I Only) 		X	X		X	X		

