4. Review and capture of all concomitant medications will be performed as indicated. Concomitant medications include prescription medications and over-the-counter preparations used by a patient within at least 14 days prior to first dose of protocol-defined treatment and continuing through at least the 28-day Follow-Up study visit. After signing informed consent, adverse events will be collected as detailed in protocol Section 12. All adverse events will be followed from initiation of study treatment for Phase I patients. For Phase II patients, adverse events will be followed from the time of the first research scan. Adverse events for all patients in both phases will be followed through at least 28 days after a patient's final protocol-directed treatment with CB-839 + panitumumab  $\pm$  irinotecan (whichever occurs last) or until initiation of another anti-cancer therapy – whichever occurs first.
5. For dose-escalation only: Dedicated surveillance and expedited reporting of Dose Limiting Toxicity (DLT) are required for 28 days after initiating protocol-indicated treatment. On Cycle 2, Day 1, satisfactory completion of the physical exam and the safety labs is required to help detect evidence of past or present DLT as having occurred during the first 28 days of protocol-indicated treatment. If intolerable delayed toxicity attributable (per sponsor-investigator judgement) to protocol treatment is detected past Day 28, then the 28-Day DLT window may possibly be extended. See protocol Section 10.1 for definition of DLTs.
6. Hematology includes white blood cell count with differential, hemoglobin, hematocrit, and platelet count. Blood Chemistry to include sodium, potassium, chloride, bicarbonate or carbon dioxide, blood urea nitrogen (BUN), creatinine, glucose, total bilirubin, AST, ALT, alkaline phosphatase (ALP), calcium, albumin, magnesium, phosphorus and total protein.

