#### **12.7.14 Reporting of Adverse Events related to Investigational PET/CT scans**

The Principal Investigator (PI) and attending nuclear medicine physician(s) will monitor the study progress and safety of the participating patients and will monitor for serious symptoms or toxicities related to the investigational imaging on an ongoing basis. The PI or their designee will undertake reporting any significant adverse events to the IRB and FDA as required. Adverse events during each research PET scan visit will be tracked using a case report form. Adverse events following each PET scan visit will be tracked using the "Adverse Event Tracking for PET Scan Studies Utilizing FDA INDs 113638 (F-FLT), 120035 (F-Fallypride), 119446 (F-FES), 120704 (C-Acetate) and 124202 (F-FSPG)" Form. Patients will be contacted by phone to determine whether they experienced any adverse events within the 24 hours following the injection of the tracer. Patients will be contacted no sooner than 24 hours after and no later than 48 hours following the time of tracer injection. Adverse events related to the investigational imaging will be immediately reported (within three working days) to the IRB and FDA as required. These adverse events will be recorded in the database maintained by the PI or their designee.

Adverse events for the purposes of the investigational imaging in this trial are defined as any unexpected medical occurrence in a subject who receives F-FSPG. The event does not necessarily have to be causally related to the PET radiopharmaceutical to qualify as an adverse event. An adverse event can be any unfavorable or unintended sign, symptom, or disease temporally associated with the injection of the radiopharmaceuticals, whether or not it is

considered related to the C-Glutamine PET/CT (optional in Phase I only) or F-FSPG PET/CT.

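### The Phase I adverse-event reporting period opens at first treatment, after the baseline scan with a first-in-human tracer used only in Phase I; other safeguards cover only part of the interval

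*Combined protocol and SAP*

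**What the plan says.** Section 12.1, under Reporting period, sets two starting points. For Phase I, adverse events "will be collected and reported from initiation of protocol-indicated treatment for Phase I patients". For Phase II: "For Phase II patients, AEs will be collected and reported from the time of the first research scan". Note 4 to the study calendar (Section 6.1) repeats the Phase I rule: "All adverse events will be followed from initiation of study treatment for Phase I patients".

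On the tracer, Section 2.6.2 says that imaging with 11C-Glutamine "will represent the first-in-human study of this tracer". The calendar row for that scan reads "Optional in Phase I only, not performed in Phase II". Section 4.5 caps the sub-study at 9 patients and gives each of them both tracers, twice before treatment and twice after one cycle. Section 6.2 allows the baseline scans up to 7 days before the first dose.

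On safety scope, the opening of Section 12.1 names research scans with 18F-FSPG only. Section 12.7.14 defines an imaging adverse event as "any unexpected medical occurrence in a subject who receives" 18F-FSPG, although the last sentence of that definition also names 11C-Glutamine.

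**The concern.** The two starting points are matched to the wrong groups. Phase II patients receive only 18F-FSPG and have the earlier start. Phase I sub-study patients are the only recipients of a tracer not previously given to humans, and they have the later one. The plan gives no reason for the difference. At stake is whether an event that follows the first exposure to the new tracer, but precedes study treatment, is recorded as an adverse event under a clear rule. The scope wording adds doubt, because someone applying the opening of Section 12.1 literally would not find 11C-Glutamine in it.

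**Working it through.** The plan states no figure to reproduce, and no power, alpha or event count is involved. The check sets the passages side by side and makes three simple counts.

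**1. Who gets which tracer, and when the period opens**
- Phase II: 18F-FSPG only; opens at the first research scan (Section 12.1).
- Phase I imaging sub-study: 11C-Glutamine and 18F-FSPG (Section 4.5); opens at first treatment (Section 12.1, note 4).
- Phase I outside the sub-study: no research scans, so the later start does no harm on this point.

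**2. Exposures before the period opens**
- Maximum 11C-Glutamine injections: 9 patients × 2 = 18.
- Given before treatment: 9 × 1 = 9, which is 9/18, or half.
- The other 9 follow cycle 1 and lie inside the period.

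**3. Length of the interval without an explicit collection rule**
- Section 12.7.14 and calendar note 20 require a call 24 to 48 hours after each tracer injection. Note 20 is attached to both tracer rows.
- Let d be the days from scan to first dose, with d ≤ 7. Taking the call at its 48-hour limit, the interval left is max(0, d − 2).
- d = 7 gives 7 − 2 = 5 days. Any d of 2 or less gives 0.
- A call at the earliest permitted time would give 7 − 1 = 6 days. The question put to the patient also concerns only the first 24 hours. The figure of about 5 days therefore assumes a call at 48 hours that picks up everything until then.

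**4. Whether other text closes the interval**
- Section 12.5.1 counts events arising after the first dose or after any protocol procedure. A baseline scan is such a procedure, so a later pre-dose event meets the definition. Section 12.1 nevertheless places it before the Phase I reporting period. The two conflict.
- Sections 2.6.2 and 7.12 promise continuous safety monitoring of 11C-Glutamine recipients. The Phase I reporting period does not carry that out before treatment.
- Note 4 also says "After signing informed consent, adverse events will be collected as detailed in protocol Section 12". That refers back to Section 12, whose Phase I start is first treatment, so it does not extend the period.
- Sections 6.2 and 6.3 schedule adverse-event review at screening and on Cycle 1 Day 1. These are occasions to ask. They do not say that a non-serious pre-dose event belongs in the Phase I record.
- Section 12.7.9 requires serious events to be reported regardless of cause and has no phase-specific start, so serious events are covered.

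**5. Tracer wording**
- The Section 12.1 scope omits 11C-Glutamine, while Section 12.4 describes the risks of both tracers.
- The Section 12.7.14 definition opens with one tracer and closes with both.
- The title of the post-scan tracking form lists five tracers by IND number; 11C-Glutamine is not among them.

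**The case against.** A reader might infer that nothing is collected before treatment in Phase I, and that events after the baseline 11C-Glutamine scan are lost. The documents do not support that. Section 12.7.14 runs its own system for every research scan visit, with no limit by phase or tracer: a case report form at the visit, the follow-up call, and ongoing monitoring by the principal investigator and nuclear medicine physicians. Adverse-event review on Cycle 1 Day 1 comes at the end of the interval, so a late event can still be elicited then. Serious events are reportable throughout.

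Two points about tracer wording are also weaker than they look. Every sub-study patient is meant to receive both tracers, so a definition tied to 18F-FSPG recipients reaches the planned 11C-Glutamine recipients, and the same definition goes on to name 11C-Glutamine. The form's title lists tracers by existing IND number, and Sections 2.6.2 and 7.12 describe the 11C-Glutamine IND as still to be sought. Its absence there is unsurprising and does not show that events go unrecorded.

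Nor do the documents show damage to that IND submission. It is expected after about 15 patients, and a sub-study capped at 9 cannot reach that number whatever the start date.

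All of this stands, and it limits the point. It does not remove the conflict over non-serious events between the call and the first dose, where the definition includes them and the reporting period does not.

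**Conclusion.** The point holds as an internal contradiction with a small, definite gap. For at most 9 patients, the general Phase I reporting period opens after the baseline scan with a first-in-human tracer. Non-serious events in the 0 to about 5 days between the call and first dose fall outside the stated period, contrary to Section 12.5.1 and to the monitoring promised in Sections 2.6.2 and 7.12. The scope in Section 12.1 and the opening of the Section 12.7.14 definition are incomplete for 11C-Glutamine.

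The size rests on three assumptions: the sub-study fills to its cap, the baseline scan may use the whole 7-day window, and the call is made by 48 hours. It also takes the calendar, Section 4.1 and Section 7.12 as governing on the use of 11C-Glutamine in Phase I only. The synopsis still lists that scan among the Dose Expansion criteria, which suggests, though it does not prove, that the reporting rule was not updated when the tracer moved.

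Dose-limiting toxicities are counted over 28 days from first dose, so that evaluation and the MTD are not touched. Neither is the Phase II response analysis.

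**What to change.** - In Section 12.1 (Reporting period) and calendar note 4, start adverse-event collection for Phase I imaging sub-study patients at the first research scan, as Phase II already does. Leave the start for other Phase I patients as it is.
- Name 11C-Glutamine scans alongside 18F-FSPG in the opening scope of Section 12.1.
- Name both tracers at the start of the imaging adverse-event definition in Section 12.7.14, and state that the post-scan tracking form applies to 11C-Glutamine.

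The cost is an amendment to wording and a few additional adverse-event entries in at most 9 patients. No visit, scan or analysis changes.

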### **4.1. Inclusion Criteria**

Patients must meet all of the following inclusion criteria to be eligible for enrollment into the study:

1. Signed and dated written informed consent.
2. Male or female  $\geq 18$  years of age.
3. Histologically or cytologically-confirmed diagnosis of metastatic *KRAS* wildtype colorectal cancer (CRC).
4. Eastern Cooperative Oncology Group (ECOG) performance status of 0 or 1.
5. In Dose Escalation, patients must have had at least one prior line of chemotherapy for advanced disease or progressed within 6 months of adjuvant therapy (prior chemotherapy and/or anti-EGFR therapy is permitted).

6. In Dose Expansion, patients must have received prior anti-EGFR therapy and achieved at least stable disease on at least one scan as their best response.
7. In Dose Expansion, patients must be willing to undergo a pre-treatment biopsy, and two research PET imaging techniques (F-FSPG), one at pre-treatment and one after one cycle of treatment.
8. In Dose Expansion, at least one measurable lesion as defined by RECIST 1.1 which can be followed by CT or MRI.
9. Adequate organ function including:
  - Absolute neutrophil count (ANC)  $\geq 1,500/\mu\text{L}$
  - Platelets  $\geq 100,000/\mu\text{L}$
  - Serum albumin  $\geq 3.0 \text{ g/dL}$
  - Serum creatinine  $\leq 2 \text{ mg/dL}$ , or calculated creatinine clearance  $> 50 \text{ mL/min}$  (per the Cockcroft-Gault formula)
  - Total bilirubin  $\leq 1.5$  times upper limit of normal (ULN)
  - Aspartate transaminase (AST) and Alanine Aminotransferase (ALT)  $\leq 5.0 \times \text{ULN}$ .
10. Women of childbearing potential (WOCBP) must have a negative serum pregnancy test within 14 days prior to receiving first dose of protocol-indicated treatment; and additionally agree to use at least 2 methods of acceptable contraception (Appendix 4) or abstain from heterosexual intercourse from the time of signing consent, and until 2 months after patient's last dose of protocol-indicated treatment.

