15. Reasonable effort should be made to complete End-of-Treatment (EOT) procedures on the day it is decided a patient will no longer receive protocol-indicated treatment. These procedures must be completed subsequent to and not later than 14 days after investigator decision to permanently discontinue protocol-indicated treatment with CB-839 + panitumumab  $\pm$  irinotecan (whichever treatment occurs last) and prior to any subsequent anti-cancer therapy.
16. At End-of-Treatment, CT/MRI required only if the previous CT/MRI was done  $>$  28 days before. At the 28 day Follow-Up visit, CT/MRI scan required only if disease progression not already documented by CT/MRI done at or before the prior EOT visit. If a patient discontinues the study for reason other than progressive disease confirmed by CT or MRI (e.g. adverse event), then CT or MRI scans of the chest, abdomen and pelvis must be continued every 8 weeks ( $\pm$  7 days) until disease progression is confirmed by imaging.
17. A Follow-up clinic visit is to be completed 28 days (+7 days) after patient's final protocol-indicated treatment with CB-839, panitumumab, or irinotecan (whichever occurs last). Documented attempt(s) should be made for patient return to the study clinic. It will not be considered a protocol deviation if the patient is physically unable to return for the follow-up visit; such circumstance should be recorded in the study documents, and as much of the follow-up information as possible should be obtained via feasible patient contact and from local and outside facilities.
18. Each patient will be followed for survival every 3 months ( $\pm$  14 days) after patient's final protocol-indicated treatment with CB-839, panitumumab, or irinotecan (whichever occurs last) until death, end of the study, until patient withdraws consent, or for a maximum of 1 year after the patient's final protocol-indicated treatment – whichever comes first. Survival contact can be made via clinic visit, chart review, obituary or similar observation (e.g. Social Security death index), or by telephone.
19. The screening F-FSPG PET/CT scan should be completed within 7 days of C1D1.
20. Patients will be contacted by phone to determine whether they experienced any adverse events within the 24 hours following the each research PET exam. Patients will be contacted no sooner than 24 hours after and no later than 48 hours following the time of tracer injection.

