## **6.2. Screening Visit Assessments**

Prior to performing any study-based procedures, patient informed consent must be obtained.

The following procedures must be completed ≤ 28 days prior to a patient's first dose of protocol-indicated treatment:

- Baseline evaluation of disease status by CT or MRI to include imaging of the chest, abdomen and pelvis

The following procedures must be completed ≤ 14 days prior to a patient's first dose of protocol-indicated treatment:

- Medical history and Demographics
- Comprehensive Physical exam, including assessment of the skin, conducted by a physician or qualified designee (i.e. physician assistant or nurse practitioner)
- ECOG Performance Status
- Height
- Weight
- Concomitant medication (prescription and over-the-counter drugs taken at least 14 days prior to intended Cycle 1, Day 1 dosing) and Adverse Event review
- Complete Blood Count (CBC) with differential (including white blood cell count with differential, hemoglobin, hematocrit, and platelet count)
- Blood Chemistry (including sodium, potassium, chloride, bicarbonate or carbon dioxide, blood urea nitrogen (BUN), creatinine, glucose, total bilirubin, AST, ALT, alkaline phosphatase (ALP), calcium, albumin, magnesium, phosphorus and total protein)
- Macroscopic urinalysis (microscopic analysis only if clinically indicated)
- Serum Pregnancy test in women of childbearing potential (as defined in Sections 6.1 and 7.9)
- An image-guided pre-treatment tissue biopsy will be collected for biomarker research for all patients enrolled in Phase II

The following procedures must be completed ≤ 7 days prior to a patient's first dose of protocol-indicated treatment:

- F-FSPG PET/CT scan (only for those patients enrolled in the optional Phase I imaging sub-study and all patients enrolled in Phase II)
- C-Glutamine PET/CT scan (only for those patients enrolled in the optional Phase I imaging sub-study)
- Pharmacokinetic (PK) blood samples will be collected during F-FSPG PET/CT scans (only for those patients enrolled in the optional Phase I imaging sub-study and all patients enrolled in Phase II). Details regarding PK collection and handling are provided in the lab manual.
- Serum pregnancy test must be performed within 24 hours prior to scheduled research scans

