## 12.5. Safety Parameters and Definitions

### 12.5.1 Adverse Event (AE)

An adverse event is any undesirable sign, symptom or medical condition or experience that develops or worsens in severity after starting the first dose of study treatment or any procedure specified in the protocol, even if the event is not considered to be related to the study.

Abnormal laboratory values or diagnostic test results constitute adverse events only if they induce clinical signs or symptoms or require treatment or further diagnostic tests.

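### Phase II adverse-event collection opens at the first research scan (Day -7 at the earliest), but the mandatory research biopsy is allowed from Day -14, so early biopsy complications can fall outside the collection window

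*Combined protocol and SAP*

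**What the plan says.** Two places set the start of Phase II adverse-event collection, and they agree. The reporting-period text in Section 12.1 states: "For Phase II patients, AEs will be collected and reported from the time of the first research scan". Note 4 to the Study Calendar (Section 6.1) states: "For Phase II patients, adverse events will be followed from the time of the first research scan".

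The timing of that scan is also set twice. Note 19 to the calendar says of the screening 18F-FSPG scan that the "PET/CT scan should be completed within 7 days of C1D1". Section 6.2 lists it under the sentence "The following procedures must be completed ≤ 7 days prior to a patient's first dose of protocol-indicated treatment".

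The biopsy stands in a different list in Section 6.2, introduced by "The following procedures must be completed ≤ 14 days prior to a patient's first dose of protocol-indicated treatment". The entry reads: "An image-guided pre-treatment tissue biopsy will be collected for biomarker research for all patients enrolled in Phase II". Section 4.1 makes it a condition of entry: "In Dose Expansion, patients must be willing to undergo a pre-treatment biopsy". Section 7.13 repeats that it applies to all Phase II patients.

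Section 12.5.1 defines an adverse event as one that "develops or worsens in severity after starting the first dose of study treatment or any procedure specified in the protocol".

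**The concern.** The biopsy is image-guided, invasive, taken for biomarker research and compulsory in Phase II. It is a protocol-specified procedure, so under Section 12.5.1 a complication that follows it is an adverse event. The reporting period nevertheless starts at a different procedure, one that may come later. A site that applies Section 12.1 as written would have no instruction to record, for example, a bleed managed as an outpatient after the biopsy and before the scan.

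The rest of Section 12 does not make up for this. Section 12.1 names the investigational treatment and the 18F-FSPG scans when it describes related events, and does not name the biopsy. Sections 12.6 and 12.6.2 ask only about the relationship to treatment. Section 12.7.14 gives the research scans their own adverse-event form and a follow-up telephone call; the biopsy has no equivalent. At stake is a complete record of harm from a procedure that patients undergo only because they are in the trial.

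**Working it through.** The plan gives no figure to reproduce. The check compares the permitted windows day by day.

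**Inputs**
- Biopsy: Day -14 to Day -1 (Section 6.2, 14-day list; calendar screening column).
- First research scan: Day -7 to Day -1 (Section 6.2, 7-day list; calendar note 19).
- Start of Phase II collection: day of the first research scan (Section 12.1; calendar note 4).
- Order of biopsy and scan: not stated anywhere.

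**Uncovered interval** = scan day minus biopsy day when the biopsy comes first, otherwise zero.

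| Biopsy day | Scan day | Uncovered days |
|---|---|---|
| -14 | -7 to -1 | 7 to 13 |
| -8 | -7 to -1 | 1 to 7 |
| -7 to -2 | any later day up to -1 | 1 to 6 |
| any day after the scan | -7 to -2 | 0 |

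The maximum is (-1) - (-14) = 13 days. For procedures on the same day, coverage depends on which is done first.

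**How many permitted schedules leave a gap**
- All biopsy/scan day pairs: 14 × 7 = 98.
- Biopsy on Day -14 to -8, always before the scan: 7 × 7 = 49.
- Biopsy on Day -7 to -2 with a later scan: 6 + 5 + 4 + 3 + 2 + 1 = 21.
- Biopsy on an earlier day than the scan: 49 + 21 = 70 of 98.
- The other 28 are 7 same-day pairs and 21 with the scan first.

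These are counts of schedules that the plan allows. They are not probabilities, because the documents do not say how sites will order the visits.

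**Definition against collection window.** Take a non-serious complication that begins the day after a Day -12 biopsy, that is, on Day -11. Under Section 12.5.1 it is an adverse event, since it follows a protocol-specified procedure. Under Section 12.1 and note 4 it predates collection by at least 4 days (Day -11 to Day -7). Both statements cannot govern the same event.

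**After the change.** If collection opens at whichever of biopsy and scan comes first, the uncovered interval after biopsy is 0 days for all 98 pairs.

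**The case against.** Several passages point the other way.

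- **Serious events.** Section 12.7.9 requires every SAE to go to the Coordinating Center within 24 hours whatever its cause, Section 12.7.13 sends all SAEs to the drug supplier, and Section 13.3 has the monitoring committee review all SAEs each quarter. This largely stands. A reader might infer that a serious biopsy complication would leave no safety record, or that the monitoring committee and IRB would be misled. The documents do not establish either. What remains is an ambiguity: Section 12.7.9 states no start date, the reporting-period text makes no exception for SAEs, and Section 12.7.3 ties death reporting to the AE reporting period, although Section 12.1 lists all deaths in its scope.
- **Screening review.** The calendar and Section 6.2 both include an adverse-event review at screening, and Section 7.4 and note 4 speak of collection after consent. Both of the latter refer to Section 12 for the detail, which leads back to the first-scan start. The screening review has no stated rule for what it records.
- **Scope of Section 12.1.** It includes a catch-all for study-specific concerns and a general statement about all adverse events, and it foresees late follow-up of procedure-related events. The scope is therefore not closed to the biopsy, but none of this moves the start date.
- **Medical history.** A reader might infer that a persisting complication would be filed as medical history. Section 12.7.4 reserves that for conditions present when the study starts, and Section 5.1 requires registration before tissue acquisition, so the text does not direct this.
- **Biopsy risks.** Their absence from Sections 12.2 to 12.4 carries little weight, since Section 12.6.1 also counts the consent document as a source of listed risks and that document is not available here.

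**Conclusion.** The point holds as a contradiction between the Phase II collection window and the plan's own definition of an adverse event. A biopsy on Day -14 to -8 always precedes collection, and one on Day -7 to -2 does so if the scan is later. The gap runs from 0 to 13 days. It is clear for non-serious complications and an ambiguity for serious ones.

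Up to 29 Phase II patients are exposed to it, or 10 if accrual stops after the first stage. The documents give no biopsy complication rate and do not fix the order of procedures, so no expected number of missed events can be stated. The conclusion rests only on reading the screening lists and the reporting-period text as written.

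A related limit is separate from the window. Section 15 restricts the safety analyses to patients who received at least one cycle, so a patient whose complication prevented dosing would be absent from them even if the event had been collected. The response endpoint, the two-stage design and the sample size are unaffected. The change is worth making because it is specific and cheap.

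**What to change.** 1. Amend the reporting-period text in Section 12.1 and calendar note 4 so that Phase II AE and SAE collection opens at the first protocol-specified research procedure, biopsy or scan. Before Day 1, collection may be limited to SAEs and procedure-related events.
2. State the same start in Section 12.7.9, so that the timing of SAE reporting is explicit. Section 12.7.3 follows, since it refers to the reporting period.
3. Name the research biopsy in the related-event scope of Section 12.1 and add it as an attribution option in Section 12.6.2.
4. In Section 15, list biopsy-related events separately for patients whom the one-cycle rule leaves out of the safety set.

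The cost is protocol wording, one attribution option on the case report form and one listing. The downside is a few more pre-treatment events to record, including for patients who have the biopsy and then fail screening.
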